Appendix 1- Calendar of Events

Procedures	Visit 0 Recruitment -14 to 0 Days	Visit 1 Baseline Assessment Week 0	Visit 2 Week 2	Visit 3 Week 4	Visit 4 Week 8	Phone Survey Week 12	Phone Survey Week 24	Responsibility
PI/C, eligiblity paperwork, exam for inclusion criteria	X							PI/Clinical Coordinator (CC)
X-Ray Scheduled	X							PI or Outside
Ultrasound Imaging		X	X	X	X			GTS
ITU Treatment		X		X				GTS
Focused Physical Exam & Clinical Grading for Epicondylitis severity		X	X	X	X			PI or CC
Subject Patient Rated Tennis Elbow Evaluation		X	X	X	X	X	X	Panelist Week 2-8 / PI or CC Weeks 12 and 24
Self-Assessment Questionnaires: Satisfaction & Improvement		X	X	X	X	X	X	Panelist Week 2-8 / PI or CC Weeks 12 and 24
Physical Therapy		X						PI or CC
Home Heat/Cold & Stretching Program Review		X	X	X	X			PI or CC
Telephone Survey						X	X	PI or CC

GUIDED THERAPY SYSTEMS, CONFIDENTIAL

Appendix 2 – PRTEE (attachment)
PATIENT-RATED TENNIS ELBOW EVALUATION

Name _____ Date _____

*The questions below will help us understand the amount of difficulty you have had with your arm in the past week. You will be describing your **average** arm symptoms **over the past week** on a scale 0-10. Please provide an answer for all questions. If you did not perform an activity because of pain or because you were unable, then you should circle a "10". If you are unsure please estimate to the best of your ability. Only leave items blank if you never perform that activity. Please indicate this by drawing a line completely through the question.*

1. PAIN in your affected arm																																		
Rate the average amount of pain in your arm over the past week by circling the number that best describes your pain on a scale from 0-10. A zero (0) means that you did not have any pain and a ten (10) means that you had the worst pain imaginable.																																		
RATE YOUR PAIN: 
 
 No Pain	Worst Imaginable	
 
											No Pain	Worst Imaginable																						
No Pain	Worst Imaginable																																	
When you are at rest	0	1	2	3	4	5	6	7	8	9	10																							
When doing a task with repeated arm movement	0	1	2	3	4	5	6	7	8	9	10																							
When carrying a plastic bag of groceries	0	1	2	3	4	5	6	7	8	9	10																							
When your pain was at its least	0	1	2	3	4	5	6	7	8	9	10																							
When your pain was at its worst	0	1	2	3	4	5	6	7	8	9	10																							
2. FUNCTIONAL DISABILITY																																		
A. SPECIFIC ACTIVITIES 
Rate the amount of difficulty you experienced performing each of the tasks listed below, over the past week, by circling the number that best describes your difficulty on a scale of 0-10. A zero (0) means you did not experience any difficulty and a ten (10) means it was so difficult you were unable to do it at all.
 
 
 No	Difficulty	Unable	
 
 	1	2	3	4	5	6	7	8	9	10	To Do	
 
											No	Difficulty										Unable		1	2	3	4	5	6	7	8	9	10	To Do
No	Difficulty										Unable																							
	1	2	3	4	5	6	7	8	9	10	To Do																							
Turn a doorknob or key	0	1	2	3	4	5	6	7	8	9	10																							
Carry a grocery bag or briefcase by the handle	0	1	2	3	4	5	6	7	8	9	10																							
Lift a full coffee cup or glass of milk to your mouth	0	1	2	3	4	5	6	7	8	9	10																							
Open a jar	0	1	2	3	4	5	6	7	8	9	10																							
Pull up pants	0	1	2	3	4	5	6	7	8	9	10																							
Wring out a washcloth or wet towel	0	1	2	3	4	5	6	7	8	9	10																							
B. USUAL ACTIVITIES 
Rate the amount of difficulty you experienced performing your usual activities in each of the areas listed below, over the past week, by circling the number that best describes your difficulty on a scale of 0-10. By "usual activities", we mean the activities that you performed before you started having a problem with your arm. A zero (0) means you did not experience any difficulty and a ten (10) means it was so difficult you were unable to do any of your usual activities.
																																		
1. Personal activities (dressing, washing)	0	1	2	3	4	5	6	7	8	9	10																							
2. Household work (cleaning, maintenance)	0	1	2	3	4	5	6	7	8	9	10																							
3. Work (your job or everyday work)	0	1	2	3	4	5	6	7	8	9	10																							
4. Recreational or sporting activities	0	1	2	3	4	5	6	7	8	9	10																							
Comments: _____																																		

Appendix 2 – PRTEE (attachment), continued

Scoring Instructions

Minimize non-response by checking forms when patients complete them. Make sure that the patient left an item blank because they could not do it, that they understand that should have recorded this item as a “10”. If patients are unsure because they have rarely performed an activity in the past week, then they should be encouraged to estimate their average difficulty. This will be more accurate than leaving it blank. If they never perform an activity they will not be able to estimate and should leave it blank. If items from a subscale are left blank, then you can substitute the average score from that subscale.

Pain Subscale- Add up 5 items.	Best score= 0; Worst score =50
Specific Activities- Add up 6 items	Best Score= 0; Worst Score = 60
Usual Activities – Add up 4 items items	Best Score= 0; Worst Score = 40
Function Subscale- (Specific Activities + Usual Activities)/2-	Best score= 0; Worst score =50
Total Score = Pain Subscale + Function Subscale	Best Score= 0 Worst Score = 100 (pain and disability contribute equally to score)

Reliability of subscales and total score are sufficiently high that both subscales and total are reportable.

© MacDermid 2005

GUIDED THERAPY SYSTEMS, CONFIDENTIAL
Appendix 3-A; Self Reported Outcome Measures

SROM 1.

Compared to your initial visit:

- I feel BETTER OFF than before treatment
- I feel THE SAME as before treatment
- I feel WORSE than before treatment

SROM 2.

Compared to your initial visit, describe your heel pain now:

- I have NO PAIN
- I have LESS PAIN than before the treatment regimen
- I have THE SAME PAIN as before the treatment regimen
- I have MORE PAIN than before the treatment regimen

SROM 3.

What percent improvement in heel pain have you experienced since starting the study?

- None
- 1 to 25%
- 26 to 50%
- 51 to 75%
- 76 to 99%
- 100%

SROM 4.

How do you rate your heel pain since the start of the study treatment?

- All better
- Much better
- Slightly better
- Unchanged
- Worse

SROM 5.

What percent improvement in overall daily function including work and/or recreational activities have you experienced since starting the study?

- None
- 1 to 25%
- 26 to 50%
- 51 to 75%
- 76 to 99%
- 100%

SROM 6.

Regarding the treatment that you received:

[figure not shown]
- I am TOTALLY SATISFIED with the treatment
- I am SATISFIED with MINOR RESERVATIONS with the treatment
- I am SATISFIED with MAJOR RESERVATIONS with the treatment
- I am DISSATISFIED with the treatment

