Subjects will receive conservative standard of care treatment plus two ITU treatments (week 0 and week 4) on the affected CET (figure 2) using the ultrasound therapy device. Treatments will be up to 10 minutes in duration. A 2, 4, and 8 week follow up period will be included to monitor the effects of the therapy post treatment. A 12 and 24-26 week telephone assessments for the primary objectives will also be included. Telephone assessments will consist of the subjects answering the survey questions over the phone.

Subject self-assessments will be conducted before the treatment phase and during the follow-up period. Physical exams will be completed by a physician. Physical therapy will be completed by a therapist. ITU treatment and diagnostic ultrasound will be performed by Guided Therapy personnel as shown in the full schedule of events (Appendix 1).

[figure not shown]

Figure 2: Treatment Area

SELECTION OF SUBJECTS**Planned number of subjects**

The study population will consist of up to 25 subjects with unilateral CET tendinosis defined as pain lasting more than 3 months with little or no improvement following conservative standard of care alone.

The selection of suitable subjects will be made according to the inclusion and exclusion criteria described in the following sections.

Inclusion Criteria

1. Subjects who are in general good health and are willing to cooperate and participate by following study requirements for the duration of the study, and to report any adverse symptoms immediately;
2. Subjects who have provided written and verbal informed consent;
3. At time of enrollment subjects are between the ages of 21 and 65 years
4. Subjects literate in English and able to complete all patient self-assessment questionnaires;

5. Subjects is willing to refrain from beginning any additional treatment during the duration of the study;
6. Subjects is willing to refrain from changing physical activity during the duration of the study;
7. Subjects diagnosed with unilateral CET tendinosis defined as pain lasting more than 3 months with little or no improvement following conservative standard of care alone.
8. Subjects with BMI ≤ 35 or at the discretion of the PI.
9. Subjects must be able to sit in a chair with their arm on an appropriate table for the treatment and diagnostic ultrasound imaging.
10. Subject must be able and willing to complete the at home therapy regimen.

Exclusion Criteria

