Subjects may discontinue from the clinical study at any time. In addition, the Principal Investigator (PI) or designee has the right to withdraw a subject for any reason that is in the best interests of the subject. The subject must inform the Investigator immediately if they intend to withdraw. Subjects may be asked to come to the study facility to complete some end of study procedures.

The Investigator can remove the subject from this study without their consent for any reason, including, but not limited to:

- His/her judgment that any condition or circumstance may jeopardize their welfare or the integrity of the study.
- Their failure to follow the instructions of the investigator(s) (protocol non-compliance)
- Subject BMI exceeds ≥ 35 during the courses of the study.
- If the study is stopped by GTS and/or Principal Investigator of the study prior to completion.

CLINICAL ASSESSMENTS

Assessment of Efficacy

Primary:

The primary endpoint(s) for efficacy and tolerability will be the total score of the PRTEE questionnaire (Appendix 2), subject self-assessment of improvement and satisfaction (SROM-Appendix 3-B), and Visual Analog Scale for Pain (VAS) or Universal Pain Assessment Tool (Appendix 3-C).

Secondary:

The secondary endpoint for efficacy will be a measured reduction in tendon thickness by diagnostic ultrasound, and a physical examination.

PRTEE Questionnaire

The PRTEE questionnaire (**Appendix 2**) evaluates three domains clinically relevant to patients (pain, function, and activity) and was specifically developed to assess the clinical severity of CET tendinopathy. It is composed of 15 questions that cover 3 domains of pain (questions 1 through 5), function for specific activities (questions 6 through 11), and general activities (questions 12 through 15). All questions are scored 0 – 10. Higher scores indicate more severe CET tendinopathy. The PRTEE questionnaire has been validated and shows good test-retest reliability¹⁸

Physical Examination

Medical History: Review patient's medical history questionnaire. Review any diagnostic imaging, tests, or work up listed under longitudinal medical record and centrality. Ask about possible trauma or history of injuries to the symptomatic arm. Review athletic history (tennis, golf, etc) and subject's pre-study exercise regimen (if any). Height, Weight (BMI) will also be documented.

History of Present Illness: Most common complaint is of elbow pain.

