
If a subject meets all the inclusion/ exclusion criteria, they will be enrolled onto the study, issued a subject number and an X-ray will be scheduled.

Visit 1 and 3: (Weeks 0 and 4) Study treatments

1. Record AEs, con meds and other events
2. Administer PRTEE-A questionnaire (Appendix 2)
3. Subject self-assessment questionnaire (Appendix 3)
4. Focused Physical Evaluation
5. Diagnostic Ultrasound images taken
6. ITU treatment, and VAS assessment of treatment tolerability.
7. Physical Therapy will be performed as described (Appendix 4 – Visit 1 only)
8. Home Cold Pack & Stretching Program review and Log (Appendix 6-A and 6-B)

Visit 2, and 4: (Weeks 2 and 8) Diagnostic Ultrasound, Self-Assessments, Physical Examination

1. Record AEs, con meds and other events;
2. Administer PRTEE-A questionnaire (Appendix 2)
3. Subject self-assessment questionnaire (Appendix 3)
4. Diagnostic Ultrasound image taken;
5. Home Cold Pack & Stretching Program review and Log (Appendix 6-A and 6-B)

Phone/Online Interviews at 3 and 6 months post treatment

1. Record AEs, con meds and other events;
2. Follow-up phone interview PRTEE-A verbally administered (Appendix 2).
3. Subject self-assessment questionnaire (Appendix 3)

STUDY TREATMENT

ITU will be performed by a trained technologist, using a clinical prototype (Ulthera FDA cleared in Sept. 2009) GEN II or GEN III designed Guided Therapy Systems, LLC. Mesa, AZ USA (Appendix 7-A).

Subjects will be treated seated with their arm resting on a structure that is comfortable for the subject and technologist. Transdermal application of ITU therapy: An average energy up to 3 joules (0.5 to 3 J) will be administered to the affected CET tendon longitudinally until the maximum number of lines (12) are reached. Each line will include individual thermal zones, less than 1 mm³ in volume, centered at a depth between 2 – 6 mm, up to 2 mm apart (figure 3).

[figure not shown]
[figure not shown]

Figure 3. Zone pitch, and depth. Tendo

Treatment pattern:

Acoustic Coupling Gel will be applied every 3-5 lines.

Figure 3-1. Zone pitch, and depth.

The study treatment will be a 10 minute session using the ultrasound therapy device with coupling gel. Subjects will be treated seated with their arm resting on a structure that is comfortable for the subject and technologist.

DIAGNOSTIC ULTRASOUND IMAGING

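### Three of the six SROM items, a named primary measure in this elbow trial, ask about heel pain

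*Protocol*

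**What the plan says.** The Primary paragraph of the protocol's Assessment of Efficacy names three measures: the PRTEE total score, "subject self-assessment of improvement and satisfaction (SROM-Appendix 3-B"), and the "Visual Analog Scale for Pain (VAS) or Universal Pain Assessment Tool (Appendix 3-C").

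The SROM form is printed in Appendix 3-A. Three of its six items name a body site, and it is the same one each time:

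- SROM 2: "Compared to your initial visit, describe your heel pain now"
- SROM 3: "What percent improvement in heel pain have you experienced since starting the study"
- SROM 4: "How do you rate your heel pain since the start of the study treatment"

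The condition under study is at the elbow. Inclusion criterion 7 reads in part "Subjects diagnosed with unilateral CET tendinosis defined as pain lasting more than 3 months", and the Study Outline gives "two ITU treatments (week 0 and week 4) on the affected CET". The SAP title refers to lateral epicondylitis.

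Appendix 1 and the Outcome measures section schedule the self-assessment at weeks 0, 2, 4, 8, 12 and 24. The last two are done remotely, under the visit heading "Phone/Online Interviews at 3 and 6 months post treatment".

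**The concern.** A question about the heel does not measure pain in the elbow. If the form was used as printed, a subject has two ways to answer. Read literally, the answer says nothing about the treated tendon. Read with elbow substituted, it says what was intended. The form does not record which reading was used, so the two kinds of answer cannot be separated at analysis.

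This matters because SROM is named as a primary measure, and these are the only items on it that ask subjects to rate change in pain directly, including a percentage improvement. A table of SROM pain results in the final report would carry the ambiguity with no means of correcting it.

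**Working it through.** There is no formula or planned figure to reproduce. The check is to read all six items, classify them, and trace the form to the endpoint definition and to the analyses.

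**Step 1: classify the items in Appendix 3-A.**

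| Item | Content | Body site named |
|---|---|---|
| SROM 1 | Overall change since the initial visit | None |
| SROM 2 | Pain now compared with the initial visit | Heel |
| SROM 3 | Percentage improvement in pain | Heel |
| SROM 4 | Rating of pain since treatment began | Heel |
| SROM 5 | Percentage improvement in daily function | None |
| SROM 6 | Satisfaction with treatment | None |

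**Step 2: count.**

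- All items: 3/6 = 50% name the heel.
- Pain items (2, 3, 4): 3/3.
- Change or improvement items (1 to 5): 3/5 = 60%.
- Satisfaction items (6): 0/1.

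These are counts of items. They do not measure an effect on any result.

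**Step 3: look for a correction.** Neither document describes a heel condition or a heel assessment, and neither tells staff or subjects to read heel as elbow. The word stands in three separate, complete questions, so it is not a PDF-reading fault or a redaction.

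**Step 4: what a literal reading does.** Take a subject with a healthy heel. On SROM 2 the natural answer is that there is no pain, which is the best category. On SROM 3 it is no improvement, and on SROM 4 it is unchanged, both unfavourable. The same literal reading pushes items in opposite directions. The documents give no basis for estimating how many subjects would read the items this way, so neither the size nor the sign of a bias can be given.

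**Step 5: trace to the analyses.** The Statistical analysis paragraph under Aim 1 names the PRTEE and the VAS. The SAP describes a pain-reduction analysis on the 10-point scale and a PRTEE score reduction. Neither specifies an analysis of SROM, so specified analyses affected: 0.

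**Step 6: other measures of elbow pain.** The PRTEE pain subscale (Appendix 2) has five items and is worded for the affected arm. The Outcome measures section ties the activity-pain VAS to the symptomatic arm. Both are untouched.

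**The case against.** The strongest reply is that this is a drafting slip with little reach. Aim 1 assigns clinical pain to the VAS and lists SROM under function, and the function item, SROM 5, names no body site. For the stated purpose of improvement and satisfaction, SROM 1, 5 and 6 still work. No planned analysis uses the three faulty items.

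Context also helps. Every subject has a one-sided elbow condition and answers the arm-worded PRTEE at the same visits. The SROM items themselves refer back to the study or its treatment. At weeks 12 and 24 site staff are responsible for the survey and could clarify. Finally, the case report form is not among the documents, so the wording actually used is unknown. The SAP describes data collection in the past tense, so revising the form may come too late.

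Much of this stands, and it limits the weight of the point. It does not remove the fault. The primary endpoint paragraph names SROM as a whole, without excluding items 2 to 4. Context makes the elbow reading likely for many subjects, but nothing shows that all used it or that staff explained the wording; an interviewer could equally read the item out as printed. If data collection is over, the reporting part of the fix still applies.

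**Conclusion.** The concern holds and should be fixed. SROM 2, 3 and 4 name the wrong body site, and as printed their answers cannot be interpreted as elbow pain with confidence. The fault is confined to those three items. SROM 1, 5 and 6, the PRTEE and the VAS are unaffected, and so are the analyses the plan specifies.

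Confidence is high for the printed wording. The effect on collected data rests on the assumption that the form was given as printed, which the documents do not settle.

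**What to change.** In SROM 2, 3 and 4, replace the heel wording with elbow pain (treated arm), and use the same text on the clinic form and in the phone or online interview. Ethics and Informed Consent requires agreement by the sponsor and the principal investigator and written IEC/IRB approval. A change to an outcome item is unlikely to qualify for that section's exception for logistical or administrative changes.

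For forms already completed with the heel wording, state the wording in the report. Then either present SROM 2 to 4 with that caveat or leave them out of statements about elbow pain. Keep SROM 1, 5 and 6.

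As a minor clerical correction, align the appendix references in the primary endpoint paragraph: SROM is cited as 3-B but printed as 3-A, and the VAS is cited as 3-C but printed as 3-B.

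The cost is a wording change to three items on one form and one approval, with no extra subjects, visits or procedures.

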TITLE: STUDY TO EVALUATE THE SAFETY, EFFICACY AND TOLERANCE OF INTENSE THERAPEUTIC ULTRASOUND (ITU) FOR THE TREATMENT OF LATERAL EPICONDYLITIS

PROTOCOL NO. and WIRB NO: 20150654

DATE: March 2, 2015

Principal Investigator: [name]

The More Foundation
[name]
[name]
[name]

Sponsor: Guided Therapy Systems
[name]
[name]

Statistical Analysis Plan:

Statistical Methods

Pain Reduction:

Pain level for subjects at the region of interest was self-reported at pre-treatment, used as baseline, and again at each follow-up at 4, 8, 12, and 26 weeks following initial treatment. The pain scale subjects used to identify their level of pain was a 10-point pain scale, where 0 = no pain, 1 = slight pain, through 10 which equates to the patients' worst imaginable pain. The goal for all subjects was to reduce pain by at least 25%. For patients reporting an initial (baseline) score ranging 6-10, this reflects a VAS pain score reduction \geq a 2 point drop; for initial scores ranging 2-5, this reflects a VAS pain score reduction \geq a 1 point drop. Pain scores reported at follow-up timepoints were compared to baseline score for each subject to determine if the goal was met by dividing the difference in the follow-up and baseline pain score by the baseline pain score. The percentage of subjects that met the pain reduction goal was calculated at each timepoint for both groups by dividing the number of subjects that achieved the pain reduction goal at that timepoint by the total number of patients that gave a pain score for that timepoint.

Patient Rated Tennis Elbow Evaluation Score Reduction:

In addition to the 10-point VAS pain scale, patients self-reported answers to questions from the Patient Rated Tennis Elbow Evaluation (PRTEE) questionnaire, which has been standardized for use in research studies to evaluate patient's level of pain and function ^[10]. Scores range from 0-100, with 0 indicating no pain and 100 indicating the worst pain imaginable in a variety of daily activities. Self-reported scores were taken at baseline and each follow-up timepoint. The average score for each timepoint were calculated, and follow-up averages were compared to baseline to calculate the percentage reduction in score.

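### SROM 3 and SROM 5 offer no answer for worsening, so a summary of these two items alone can show only no change or benefit; the gap matters most for function (SROM 5)

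*Protocol*

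**What the plan says.** The protocol's Assessment of Efficacy section lists three primary measures: the PRTEE total, a pain VAS, and "subject self-assessment of improvement and satisfaction (SROM-Appendix 3-B". That reference points to Appendix 3-B, but the SROM items are printed under Appendix 3-A.

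In Appendix 3-A, SROM 3 asks "What percent improvement in heel pain have you experienced since starting the study" and SROM 5 asks "What percent improvement in overall daily function including work and/or recreational activities have you experienced since starting the study". Both offer the same six answers: None, four bands covering 1 to 99%, and 100%. Three other items on the form do allow for decline. SROM 1 includes "I feel WORSE than before treatment", SROM 2 includes "I have MORE PAIN than before the treatment regimen", and SROM 4 ("How do you rate your heel pain since the start of the study treatment") ends with Worse. SROM 6 asks about satisfaction with the treatment received. SROM 2, 3 and 4 refer to the heel, although this is an elbow trial.

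The procedure list shared by Visits 1 and 3 has "Subject self-assessment questionnaire (Appendix 3" as step 3 and ITU as step 6. Appendix 1 confirms the improvement and satisfaction questionnaires at Visit 1.

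The protocol's Statistical analysis paragraph names only the PRTEE and the VAS for assessment before and after intervention. The SAP covers only VAS response and the percentage reduction in average PRTEE. Neither document gives a code, summary or test for any SROM item.

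**The concern.** Items that ask only how much better a subject is, with None as the lowest answer, merge two different outcomes: no change and decline. Since SROM is named as primary, a report could present a mean percent improvement or a distribution from items 3 and 5. Such a summary could not fall below zero, whatever happened to the subjects.

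The stake is greatest for function. SROM 5 is the only SROM item that asks specifically about it, so a subject who loses function has no direct way to say so on this form. With up to 25 subjects, a few who decline would matter.

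Timing adds a smaller problem. At Visit 1 the form comes before any ITU, so its improvement and satisfaction answers carry no information about the treatment. Pooled with later answers, they would only dilute or confuse a summary.

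**Working it through.** **1. Is there a stated figure to reproduce?** No. The documents give no figure for any SROM item. The planned 25 subjects (two-sided alpha 0.05, 80% power) have no endpoint, effect size or SD attached, and this point does not depend on that number.

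**2. Which instruments can record decline?**

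| Measure | Subject | Answer or direction for worse? |
|---|---|---|
| SROM 1 | overall | yes |
| SROM 2 | pain (heel wording) | yes |
| SROM 3 | pain (heel wording) | **no** |
| SROM 4 | pain (heel wording) | yes |
| SROM 5 | daily function | **no** |
| PRTEE total, 0 to 100 | pain and function, 50 points each | yes, the score can rise from baseline |
| VAS, 0 to 10 | pain | yes, the score can rise from baseline |

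For pain, SROM 2 and 4 would cover the gap in SROM 3 if they asked about the elbow. For function, no other SROM item does so.

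**3. Direction of the effect, with no distribution assumed.** Let X be a subject's true percent change, positive for better. Suppose None is read as 0. The item then records max(0, X), and the mean is overstated by E[max(0, X)] − E[X] = E[max(0, −X)]. This is above zero whenever anyone declines.

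A count shows it. If 13 of 25 subjects worsen by 30% and 12 improve by 30%:
- true mean = (12 × 30 − 13 × 30) / 25 = −1.2%
- recorded mean = (12 × 30 + 13 × 0) / 25 = +14.4%

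**4. Size, under assumptions.** The documents give no mean, SD or shape. Assume X is normal with mean m and SD s. Then E[max(0, X)] = m Φ(m/s) + s φ(m/s).

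| Assumed true mean | Assumed SD | Recorded mean | Overstatement |
|---|---|---|---|
| 0 | 20 | 0.399 × 20 = 8.0 | 8.0 |
| 0 | 30 | 0.399 × 30 = 12.0 | 12.0 |
| 0 | 40 | 0.399 × 40 = 16.0 | 16.0 |
| −10 | 20 | 4.0 | 14.0 |
| −10 | 30 | 7.6 | 17.6 |
| −10 | 40 | 11.5 | 21.5 |
| +30 | 30 | 30 × 0.841 + 30 × 0.242 = 32.5 | 2.5 |

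The result depends on the assumed mean as much as on the SD. It is large when the true effect is near or below zero and small when most subjects improve.

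**5. Timing.** Step 3 precedes step 6 at both treatment visits. At Visit 3 the subject has already had one treatment, so the answers mean something. At Visit 1 the subject has had none.

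**The case against.** The strongest reply is that the six SROM items work together. SROM 1 gives the direction, items 3 and 5 give the size of any improvement, and None is a truthful answer from someone who got worse. The PRTEE, also primary, is given at every SROM time point, can move either way, and devotes half its total to function. The SAP states its range as "Scores range from 0-100, with 0 indicating no pain and 100 indicating the worst pain imaginable in a variety of daily activities". Exacerbation of a pre-existing condition also counts as an adverse event.

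Most of this stands, and it rules out three stronger readings that a reader might infer:

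- **That worsening cannot appear in the primary results.** It can, in SROM 1, the PRTEE and the VAS data.
- **That decliners are scored as zero change, or that a test is biased.** No SROM coding, mean or test is planned in either document. Reading None as 0 in the working is an assumption.
- **That the bias is 8 to 16 points.** That range fixes the true mean at zero. Every subject also follows an exercise programme that the protocol expects to relieve pain in most cases, so a positive mean is plausible and the overstatement could be much smaller.

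Nor can one say flatly that a comparator is absent. The protocol gives ITU to all subjects, but the SAP refers to two groups without defining them.

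Two things remain. The absence of an SROM rule also means that nothing stops a mean percent improvement from being reported. And the planned summaries do not count decliners: the VAS response rate treats unchanged and worse subjects alike as not meeting the goal, and the PRTEE average shows only net movement of the group.

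**Conclusion.** The point holds in limited form. SROM 3 and SROM 5 cannot separate decline from no change, and any summary of these two items alone can show only zero or benefit. This follows from the form itself and needs no assumption. The gap is most serious for SROM 5.

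The size of any bias cannot be derived from the documents. The illustrations run from about 2.5 points (mean +30, SD 30) to 8 to 16 points (mean 0, SD 20 to 40), and more if the group truly worsens. They rest on normal changes, on None read as 0, and on someone choosing to average these items. This is a modest defect of form and reporting, worth correcting because the form belongs to a primary measure and the correction is cheap.

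**What to change.** - **Form.** Add a Worse category to SROM 3 and SROM 5, separate from None (no change). In the same revision, change heel pain to elbow pain in SROM 2, 3 and 4, and align the primary endpoint's appendix reference with the form.
- **SAP.** State that items 3 and 5 are reported as category counts at each time point, including the percentage worse, with no mean percent improvement.
- **Forms already completed.** Cross-tabulate None on items 3 and 5 with the worse answer on SROM 1 and with change in the PRTEE function subscale. SROM 2 and 4 are poor cross-checks because of their heel wording.
- **Visit 1.** Exclude pre-treatment SROM answers from all summaries.

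The cost is one tick-box on two items, a form revision with IRB notification, and a short SAP paragraph. Answers on the old and new forms are not fully comparable and must be reported separately or with a note.

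### The self-reported improvement items, part of the primary endpoint, use inconsistent and partly undefined starting points, so some may count change that occurred before the first ITU treatment

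*Protocol*

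**What the plan says.** The protocol's Assessment of Efficacy section lists three primary measures: the PRTEE total score, "subject self-assessment of improvement and satisfaction (SROM-Appendix 3-B"), and the VAS or Universal Pain Assessment Tool. The SROM form itself is headed Appendix 3-A; Appendix 3-B holds the pain scale.

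The SROM items are anchored as follows:

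- SROM 1 and 2 open with "Compared to your initial visit". Neither document defines that visit. The answers to SROM 1 compare with the time before treatment. The comparative answers to SROM 2 do the same for the regimen, for example "I have LESS PAIN than before the treatment regimen".
- SROM 3 asks "What percent improvement in heel pain have you experienced since starting the study".
- SROM 5 asks "What percent improvement in overall daily function including work and/or recreational activities have you experienced since starting the study".
- SROM 4 asks for a rating "since the start of the study treatment".
- SROM 6 covers satisfaction only and has no reference point.

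The Calendar of Events (Appendix 1) heads its first column "Visit 0 Recruitment -14 to 0 Days" and labels Visit 1 as the baseline assessment at Week 0. Under Assessments at Each Visit, consent and enrolment belong to Visit 0 and the first ITU to Visit 1. The PRTEE is first given at Visit 1 before ITU. The SROM is listed at that same visit, also before ITU.

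In the SAP, pain "was self-reported at pre-treatment, used as baseline", and PRTEE follow-up averages are compared with baseline. The SAP contains no SROM analysis.

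**The concern.** An improvement question measures change from whatever moment the subject has in mind. Here the form points to three moments, and two of them (the initial visit and the start of the study) are undefined. A subject enrolled at Visit 0 can reasonably take that day as the start of the study. Change between Visit 0 and the first ITU then enters the answer, although the PRTEE and VAS leave it out.

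At stake is how one of three primary measures can be read. The protocol describes no untreated group of subjects, so a comparison between groups cannot cancel change that came before treatment. The protocol does separate this interval for safety: events after consent but before the first ITU or study procedure are treated as medical history unless they worsen. The SROM has no matching rule for improvement, and the SAP does nothing to tie the items to Visit 1.

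**Working it through.** The plan gives no figure on this point to reproduce. Its sample size of 25 does not enter the check.

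**Step 1: set each item beside the schedule.**

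| Measure | Anchor in the stem | Anchor in the answers | Can it reach back before Visit 1? |
|---|---|---|---|
| SROM 1 | initial visit | before treatment | only if the initial visit means Visit 0 and the subject follows the stem |
| SROM 2 | initial visit | before the regimen | as SROM 1 |
| SROM 3 | start of study | none | yes, if read as enrolment |
| SROM 4 | start of treatment | none | no |
| SROM 5 | start of study | none | yes, if read as enrolment |
| PRTEE | Visit 1, before ITU | not applicable | baseline is pre-treatment |
| VAS | pre-treatment | not applicable | baseline is pre-treatment |

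SROM 3 and 5 are exposed on a natural reading. SROM 1 and 2 are ambiguous. SROM 4 already agrees with the other two primary measures.

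**Step 2: how much extra time can be included.**

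Inputs:

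- r = days from Visit 0 to Visit 1, from 0 to 14 (Calendar of Events). The 7-day column is an illustrative midpoint.
- w = follow-up week: 2, 4, 8, 12 or 24 (protocol, Outcome measures).

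Share of the recalled interval that precedes any ITU = r / (r + 7w).

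| Week | r = 0 | r = 7 | r = 14 |
|---|---|---|---|
| 2 | 0% | 7/21 = 33% | 14/28 = 50% |
| 4 | 0% | 7/35 = 20% | 14/42 = 33% |
| 8 | 0% | 7/63 = 11% | 14/70 = 20% |
| 12 | 0% | 7/91 = 8% | 14/98 = 14% |
| 24 | 0% | 7/175 = 4% | 14/182 = 8% |

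The SAP puts the last pain follow-up at week 26; the share there would be at most 14/196 = 7%.

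**Step 3: what the planned data could show.** At Week 0 the SROM precedes ITU, so w = 0 and the whole interval since enrolment is pre-treatment. Any improvement ticked on SROM 3 or 5 at that visit cannot be due to ITU. The schedule therefore offers a partial view of pre-treatment change, but neither document says how those answers are to be used.

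**Step 4: what the table does not show.** These are shares of elapsed time, not of improvement. The documents give no data on change between Visit 0 and Visit 1, so the shares cannot be turned into a bias.

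**The case against.** The strongest reply is that this is a wording fault with no demonstrated effect on a planned result. Several parts of that reply stand.

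- A reader might infer that four of the five improvement items are biased. The documents do not support that. The answers to SROM 1 and 2 point to the time before treatment, and the calendar names Visit 0 recruitment and Visit 1 baseline, so the initial visit need not be Visit 0. Even for SROM 3 and 5 a subject could take Week 0 as the start.
- A reader might infer that spontaneous settling before treatment is likely. That is an assumption. Inclusion criterion 7 asks for over three months of pain that has barely responded to conservative care, and study physical therapy and the home programme start only at Visit 1.
- A reader might infer that pre-treatment drift could not be seen. The Week 0 SROM could show it.
- A reader might infer that a planned percentage or test would be distorted. The SAP plans neither for the SROM, so the effect is on interpretation.

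Two further arguments carry less weight. The PRTEE asks about the past week, so its baseline is an average and not a point in time; but at Visit 1 that week lies wholly before treatment. The protocol counts the SROM among its validated forms, which argues for caution in changing it; but SROM 2 to 4 ask about heel pain in an elbow trial and need editing in any case.

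None of this supplies a common anchor. The form still leaves each subject to choose one, and the lack of an SROM analysis means the SAP does not settle it either.

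**Conclusion.** The inconsistency is real and of low severity. SROM 3 and 5 may count change before the first ITU as improvement. SROM 1 and 2 may do so, depending on how the initial visit is understood. SROM 4 does not.

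The size is unknown. It is zero when Visits 0 and 1 fall on the same day. At most, 14 extra days are recalled, and that matters most at week 2 and least at week 24. An effect requires three things: a gap between the visits, subjects who read the start of the study as enrolment, and actual change in that gap. The documents establish only that the first is possible and the second natural. They are silent on the third.

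It would be wrong to read the time shares as the amount of improvement misattributed, or to conclude that the SROM results are invalid.

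**What to change.** - **Form.** Use one anchor, for example *just before your first ultrasound treatment*, in the stems and answers of SROM 1, 2, 3 and 5. Keep SROM 4 consistent with it. In the same edit, change heel pain to elbow pain in SROM 2, 3 and 4.
- **SAP.** State that SROM improvement is measured from Visit 1 before ITU. Tabulate any improvement reported on the Week 0 SROM separately, as pre-treatment change, and do not count it as response.
- **Forms already completed.** An SAP sentence cannot re-anchor answers already given. For those, state the ambiguity when SROM 1, 2, 3 and 5 are reported, show the Week 0 answers beside them, and note that SROM 4 is the item whose anchor matches the PRTEE and VAS baseline.

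The cost is a small change of wording to a form the protocol calls validated, plus a short addition to the SAP. No visit, procedure or sample-size change is needed.
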